### 7 Study Procedures/Evaluations

### 7.1 Medical History

A complete medical history will be taken from all subjects to cover all of the inclusion and exclusion criteria. Source documentation for previous treatment (to include SOC during screening), diagnosis, and interventions should be included in the subject's records to facilitate source documentation monitoring.

### 7.2 Physical Examination

Full physical examination (all systems) must be performed by the principal investigator or sub-investigator (medically qualified professional per the local guidelines) at the Screening Visit. Wound examinations shall be performed at every visit. The examination should include examination of body systems where there are symptom complaints by the subject.

### 7.3 Adverse Event Monitoring

The PI will assess adverse events (AEs) by spontaneous, unsolicited reports of subjects, by observation, and by routine non-leading questions (e.g., "How have you felt since I last saw you?").

### 7.4 Laboratory Evaluations

Blood will be collected at the Screening Visit and End of Study Visit for routine laboratories:

- Albumin
- BUN/Creatinine/ Total protein
- Hemoglobin A1C
- Complete Blood Count
- Liver Function Tests (Alanine AminoTransferase, Aspartate AminoTransferase AST, Alkaline Phosphatase) and
- Urine Pregnancy test (for women of childbearing potential) only done at Screening

### 7.5 Target Wound Evaluations

Vascular Assessment: Ankle-Branchial Index (ABI) of ulcers/wounds will be measured using the MESI ABPI MD device. It is an automated machine that uses oscillometry and volume plethysmography for accurately calculate the ABI. This device can also automatically collect pulse volume waveform readings (see **Appendix 6A** for details).

Wound Measurement and Photography: Swift Medical wound platform will be used for the measurement and imaging of ulcers/wounds (see **Appendix 6B** for details).

### 7.6 Quality of Life Assessment

The Wound-QoL is a short questionnaire that measures the quality of life in subjects with chronic wounds. It contains the core content of three established wound questionnaires but is much shorter, and relates explicitly to the wound in each item, thereby measuring disease specific quality of life information. Results of a virtual validation indicate good reliability and validity.

The questionnaire will be completed by the subject during Treatment Visit Week 1 and the End of Study Visit (see **Appendix 5** for details).

The quality of life data will be summarized by average score at Week 1 (Baseline) and End of Study (Week 12) for each indication (DFU/VLU) and subscale (Body, Psyche and Everyday Life). Change from baseline will also be summarized. Also, the average score will be compared for both the TEST and SOC for each indication by the subscale.

### 8 Potential Risks and Benefits

#### 8.1 Potential Risks

During a preliminary clinical evaluation of the Omeza® Products Bundle, a variety of subjects and wounds received treatment with the lidocaine lavage, the collagen matrix and the skin protectant.

No serious or adverse effects have been observed to date, including hypersensitivity reactions, infection or pain. One patient stated the odor was a bit strong but tolerable. Potential concerns include hypersensitivity reaction, maceration due to combination of wound exudate with Omeza® components, or sensitivity to odor from the products.

#### 8.2 Potential Benefits

There is a public health need for products for the treatment of chronic lower extremity ulcers. The incidence of ulceration is rising as a result of the ageing population and increased risk factors for atherosclerotic occlusion such as smoking, obesity, and diabetes. Chronic ulceration of the lower extremities is a relatively common condition amongst adults, and ulcer symptoms usually include increasing pain, friable granulation tissue, foul odor, and wound breakdown instead of healing. This results in social distress and considerable healthcare and personal costs. Faster and more effective treatment protocols are needed to improve the quality of life for these subjects.

It is the goal of this trial to demonstrate that the TEST product (Omeza® Products Bundle) can be an effective addition to provide a clinical benefit for the treatment of chronic leg ulcers.

Over the past two plus years, clinical evaluation of Omeza products has been conducted in private physician office, hospital based wound center and patient home settings. The products that have been evaluated include the lidocaine lavage, collagen matrix, slow release hydrocolloid and emollient skin protectant.

In the time frame mentioned, encouraging results have been observed over a range of subjects and with a variety of wound types. Additionally, no adverse effects have been observed and subjects have generally expressed strongly favorable opinions of the products, including ease of application and overall tolerability.

### 9 Assessment of Safety

### 9.1 Adverse Event Recording/Documentation

At each contact with the subject, information regarding adverse events will be elicited by appropriate questioning and examinations. All events, both expected/unexpected and related/unrelated will be recorded on a source document. Source documents will include progress notes, laboratory reports, consult notes, phone call summaries and data collection tools. Source documents will be reviewed in a timely manner by the research team. All reportable adverse events that are identified will be recorded on the eCRF. The start date, the stop date, the severity of each reportable event, the PI's judgment of the AEs relationship and expectedness to the TEST products and the outcome will also be recorded. Adverse event reporting will extend from signing of ICF until completion of final visit.

#### 9.2 Definitions

An adverse event is any untoward medical occurrence in a subject or clinical investigation subject administered a TEST product, and which does not necessarily have to have a causal relationship with this treatment. An AE can therefore be any unfavorable and unintended sign (including abnormal laboratory finding), symptom, or disease temporally associated with the use of an investigational product, or study

procedure whether or not considered related to the TEST product. All AEs that occur prior to administration of study TEST product (blinded medical product) will not be considered a Treatment Emergent Adverse Event (TEAE) but will be recorded in the medical history.

A TEAE is defined as an AE that begins or that worsens in frequency and/or severity after at least one dose of study agent has been administered.

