## 10.3 Safety Analyses

The number and percent of subjects reporting treatment-emergent adverse events (TEAEs) will be tabulated as treated. Subjects discontinuing study product due to adverse events will be listed as will subjects reporting any serious adverse events. TEAEs will also be summarized according to severity and for the subset with at least possible relationship to study product.

Physical examination and laboratory results will also be summarized as treated. Descriptive statistics on the data at each visit and changes from baseline at each visit will be presented.

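### Section 9.2 ties adverse events and the pre-treatment cut-off to the TEST product and then defines a TEAE by an inconsistently used term, so treatment emergence in the SOC arm is contradictory and relatedness is judged for one arm only

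*Protocol*

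**What the plan says.** Protocol section 9.2 makes three statements that decide which events count.

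1. The AE definition opens: "An adverse event is any untoward medical occurrence in a subject or clinical investigation subject administered a TEST product". It later widens to events "temporally associated with the use of an investigational product, or study" (the phrase goes on to name a procedure).
2. The exclusion sentence reads: "All AEs that occur prior to administration of study TEST product (blinded medical product) will not be considered a Treatment Emergent Adverse Event (TEAE"), and continues "but will be recorded in the medical history".
3. The TEAE definition itself, up to its last two words, reads: "A TEAE is defined as an AE that begins or that worsens in frequency and/or severity after at least one dose of study agent has".

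Other sections treat safety as a matter for both arms. Section 2 makes safety compared with SOC the first secondary objective. Section 9.1 states "Adverse event reporting will extend from signing of ICF until completion of final visit". Section 10.1 puts every randomized subject with at least one study treatment in the Safety Population. Section 10.3 states "The number and percent of subjects reporting treatment-emergent adverse events (TEAEs) will be tabulated as treated", and adds a summary of the TEAEs with at least a possible relationship to study product.

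The investigator's judgement of relationship and expectedness (section 9.1) and the causality assessment (section 9.3) are both made against the TEST product.

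**The concern.** TEST means the Omeza bundle, and the SOC arm is not assigned it. A definition that starts with subjects "any untoward medical occurrence in a subject or clinical investigation subject administered a TEST product", and a cut-off set at the first TEST product, fit an arm that receives the product. They give the other arm no cut-off. The parenthetical reference to a blinded product does not fit an open-label trial.

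Two things are at stake. First, the SOC column of the TEAE tables depends on which sentence of section 9.2 is followed. Second, the exclusion sentence is also a recording instruction. Appendix B schedules medical history at Screening only, while section 9.1 attaches severity, relationship, expectedness, outcome and dates to events entered as AEs. An SOC event filed as medical history under the exclusion sentence might lack those fields, and a later analysis plan could not reliably restore them.

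**Working it through.** The protocol gives no expected adverse event rate and no safety power, so there is no figure of its own to reproduce. The check is mainly one of wording.

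**Step 1: who receives the TEST product.** The synopsis plans 26 TEST and 13 SOC subjects per indication. Over two indications that is 2 × 26 = 52 TEST and 2 × 13 = 26 SOC, 78 in total. One third (26/78) are not assigned the TEST product.

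**Step 2: each sentence of section 9.2 applied to an SOC event after the first SOC treatment.**

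| Text | Anchor | Does the SOC event count? |
|---|---|---|
| AE definition, opening | TEST product | No, read literally |
| AE definition, later clause | Investigational product or study procedure | Arguably yes, through study procedure |
| Exclusion sentence | First TEST product | No, read literally: no TEST product has been given |
| TEAE definition | Study agent | Depends on the meaning of study agent |

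**Step 3: what study agent means.** Section 5 is headed Study Agent/Interventions and lists SOC under Identity. Section 5.4, on dosage and administration of study agent, covers both TEST and SOC. In section 9.3, under the category Related, the term becomes TEST study agent and alternates with TEST product. The first usage admits the SOC event and the second does not. Even on the first usage, the TEAE definition conflicts with the exclusion sentence directly before it, and the protocol does not say which governs.

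**Step 4: relatedness.** Section 9.1 records relationship and expectedness to the TEST products. Section 9.3 frames the causality assessment around the TEST product. An SOC event thus has no assigned treatment against which it can be judged possibly related. The section 10.3 subset can fill for TEST but has no equivalent meaning for SOC.

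**Step 5: size under the literal exclusion sentence.** SOC shows 0/26 TEAEs (0/13 per indication) whatever happens. To show what that could look like, assume the same true rate in both arms. The rates are assumptions; section 8.1 reports only that no adverse effects had been observed so far. With k events, all counted in TEST, the probability of that table is C(52,k)/C(78,k). The two-sided Fisher p adds the other-tail tables that are no more probable.

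| Assumed rate | TEST shown | SOC shown | SOC if counted from first SOC treatment | C(52,k)/C(78,k) | Fisher p, literal rule |
|---|---|---|---|---|---|
| 10% | 52 × 0.10 = 5.2, about 5 | 0/26 | 2.6, about 3 | 0.123 | 0.16 |
| 20% | 52 × 0.20 = 10.4, about 10 | 0/26 | 5.2, about 5 | 0.0126 | 0.026 |
| 30% | 52 × 0.30 = 15.6, about 16 | 0/26 | 7.8, about 8 | 0.0006 | 0.0008 |

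With SOC events counted from the first SOC treatment, Fisher p is 1.0 in every row. The distortion would run against the sponsor's own product.

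**The case against.** A reader might infer that no SOC event can ever be a TEAE and that the safety comparison is void. The case against that inference is strong, and most of it stands.

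- The only sentence that actually defines a TEAE uses study agent, and section 5.4 applies that term to both arms. On that usage, SOC events after the first SOC treatment are TEAEs. This stands, but section 9.3 uses the same term for TEST alone, so it shows ambiguity and does not settle the matter.
- It is strained to call every event in an SOC subject prior to an administration that never happens. The sentence more naturally separates pre-treatment from on-treatment events, and the mention of blinding may be wording carried over from elsewhere. That is plausible, but the sentence is still the stated rule and still conflicts with the next one.
- Events are elicited at each contact, from consent to final visit, without limit by arm, and start dates are recorded. Appendix B has AE assessment at every treatment visit, and the Safety Population includes SOC. Treatment emergence can be derived for both arms if the events are entered as AEs. This stands and rules out calling the comparison void.
- The p-values rest on assumed rates and on a test that the protocol does not plan; safety is summarized by counts and percentages. At 10% the illustration is not significant. This stands, so the figures serve only as illustration.
- No passage asks sites to decide treatment emergence, so inconsistent practice between sites is conjecture. This stands. The narrower risk is the instruction to use medical history.

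None of these points answers the relatedness problem, which does not depend on how study agent is read.

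**Conclusion.** The point holds as a contradiction in stated rules. Section 9.2 anchors the AE definition and the pre-treatment cut-off to a product that 26 of 78 subjects are not assigned. It calls that product blinded in an open-label trial, and then defines a TEAE by a term that the protocol uses in two senses. Treatment emergence in SOC can therefore be read in either direction. On the literal reading of the exclusion sentence the SOC count is fixed at 0/26, and SOC events may be misrouted to medical history. On the section 5.4 reading SOC events count normally.

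Relatedness assessed against TEST alone is a one-arm measure, so the subset with at least a possible relationship cannot support the comparison in the secondary safety objective.

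The documents do not show that SOC TEAEs are impossible or that the comparison is lost. The 0/26 follows from the literal exclusion sentence alone and needs no rate assumption. The TEST counts and p-values depend on the assumed equal rates of 10% to 30%.

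**What to change.** - Define an AE as any untoward medical occurrence in a consented subject in either arm.
- Define a TEAE as an AE that starts or worsens after the first randomized study treatment, TEST or SOC, at Treatment Visit Week 1, and use that one term throughout.
- Delete the reference to a blinded medical product.
- Record events between consent and first treatment as pre-treatment AEs in both arms, in line with section 9.1, instead of moving them to medical history.
- Assess relationship to the assigned study treatment or a study procedure in both arms, and reword sections 9.1, 9.3 and 10.3 to match.

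The cost is protocol wording and eCRF guidance, including the label of the relationship field. No new visits, tests or data collection are needed. Because part of the text instructs sites where to record events, the change should come before further events are recorded and should not wait for the analysis stage.

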#### 9.3 Assessment of Adverse Events

Each AE will be assessed by the investigator with regard to the following categories.

#### Seriousness

A serious adverse event (SAE) is defined as any untoward medical occurrence that at any dose:

- Results in death.
- Is life-threatening; (This means that the subject is at risk of death at the time of the event; it does not mean that the event hypothetically might have caused death if it were more severe).
- Requires hospitalization or prolongation of existing hospitalization.
- Results in persistent or significant disability or incapacity.
- Is a congenital anomaly or birth defect.
- Is an important medical event(s) that may not be immediately life-threatening or result in death or hospitalization but that may jeopardize the subject or require intervention to prevent one of the above outcomes.

Medical and scientific judgment should be exercised in deciding whether a case is serious and whether expedited reporting is appropriate.

#### Intensity (Severity)

Investigators should assess the severity of AEs according to CTCAE, provided to each clinical site before the start of the study. In general, CTCAE version 4.0 Severity Grades are:

- Grade 1: Mild; asymptomatic or mild symptoms; clinical or diagnostic observations only; intervention not indicated
- Grade 2: Moderate; minimal, local or noninvasive intervention indicated; limiting age appropriate instrumental Activities of Daily Living (ADL) (Instrumental ADL include preparing meals, shopping for groceries or clothes, using the telephone, managing money, etc.)
- Grade 3: Severe or medically significant but not immediately life-threatening; hospitalization or prolongation of hospitalization indicated; disabling; limiting self-care ADL (Self-care ADL include bathing, dressing and

undressing, feeding self, using the toilet, taking medications, and not bedridden.)

Grade 4: Life-threatening consequences; urgent intervention indicated

Grade 5: Death related to AE

It is important to distinguish between serious and severe AEs. Severity is a measure of intensity whereas seriousness is a regulatory definition as per the CTCAE **Section 6.2.1.2**. An AE of severe intensity may not necessarily be considered serious (by definition) or a mild AE (mild stroke) may be considered as an SAE.

#### Causality

The investigator will assess the causality/relationship between the study TEST product and the AE and record that assessment on the eCRF. The causal relationship of the AE to study TEST product will be described in terms of the following:

#### Related:

This category applies to those AEs that, after careful medical consideration are felt to be related to the administration of the study agent. The relationship of an AE to the TEST study agent can be considered related if:

It follows a reasonable temporal sequence from administration of the TEST product.

It could not be reasonably explained by the known characteristics of the subject's clinical state, environmental or toxic factors or other modes of therapy administered to the subject.

It follows a known response pattern to the suspected TEST product.

It reoccurs upon re-challenge with the study TEST product.

#### Probable:

This category applies to those AEs that, after careful medical consideration, are felt with a high degree of certainty to be related to the administration of the study TEST product. The relationship of an AE to the study TEST product can be considered probable if:

It follows a reasonable temporal sequence from administration of the TEST product.

It could not be reasonably explained by the known characteristics of the subject's clinical state, environmental or toxic factors or other modes of therapy administered to the subject.

It follows a known response pattern to the investigational TEST product.

#### Possible:

This category applies to those AEs that, after careful medical consideration, are felt unlikely to be related to the administration of the study TEST product, but the possibility cannot be ruled out with certainty. The relationship of an AE to the study TEST product can be considered possible if:

It follows a reasonable temporal sequence from administration of the study TEST product.

It could be reasonable explained by the subject's clinical state, environmental or toxic factors or other therapies administrated to the subject.

It follows a known pattern of response to the investigational TEST product.

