#### Unlikely:

This category applies to those AEs that, after careful medical consideration, are felt unlikely to be related to the administration of the study TEST product. The relationship of an AE to the study TEST product can be considered unlikely if:

It does not follow a reasonable temporal sequence from administration of the study TEST product.

It could be reasonably explained by the subject's clinical state, environmental or toxic factors or other therapies administrated to the subject.

It does not follow a known pattern of response to the investigational TEST product.

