#### Not related:

The AE does not meet any of the above criteria for relatedness.

There is sufficient information that the etiology of the AE is not related to the study TEST product.

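### The causality scale in Protocol 9.3 leaves a first-time product reaction without a defined category, and it words Possible almost like Unlikely although the related-event table is cut between them

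*Protocol*

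**What the plan says.** Under Causality, Protocol 9.3 gives each category a lead judgement and then a list of items.

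- **Related** lists plausible timing, no reasonable other explanation, a pattern item ("It follows a known response pattern to the suspected TEST product") and rechallenge ("It reoccurs upon re-challenge with the study TEST product").
- **Probable** lists the first three of these, without rechallenge.
- **Possible** covers events that "are felt unlikely to be related to the administration of the study TEST product, but the possibility cannot be ruled out with certainty". Its items are plausible timing, a reasonable other explanation, and "It follows a known pattern of response to the investigational TEST product".
- **Unlikely** covers events that "are felt unlikely to be related to the administration of the study TEST product". Its items are timing that does not fit, a reasonable other explanation, and no known pattern.
- **Not related** has two items: "The AE does not meet any of the above criteria for relatedness", and sufficient information that the cause lies elsewhere.
- **Not assessable** is for insufficient or contradictory information.

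No category says whether its items are all required or whether one is enough.

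On prior experience, 8.1 states: "No serious or adverse effects have been observed to date, including hypersensitivity reactions, infection or pain". It names hypersensitivity, maceration and sensitivity to odor only as potential concerns. Section 8.2 repeats that no adverse effects were seen.

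The scale is used in 10.3, where treatment-emergent events are also summarised "for the subset with at least possible relationship to study product". It also bears on 9.4, where follow-up of serious events to resolution and reporting of serious events after the study depend on the judged relationship.

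**The concern.** There are two separate problems. First, Possible and Unlikely start from the same judgement, and only a rider about residual uncertainty separates their leads. The 10.3 summary is cut exactly there, so the boundary that matters most is the least clearly drawn. This does not depend on how the listed items are combined.

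Second, every category at or above the cut lists a known response pattern, and the protocol reports that no reaction to these products has been seen. A safety assessment of a new product should be able to place a reaction that nobody has seen before. If it cannot, the attribution of that reaction depends on how each of up to 3 sites reads 9.3.

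Causality is assigned at the site and entered on the eCRF, so a later analysis plan cannot recover it. At stake are the summary of at least possibly related events among the 52 planned TEST subjects (2 indications × 26) and the parts of 9.4 that depend on causality.

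**Working it through.** The protocol gives no figure to reproduce. The check is a comparison of wording followed by an enumeration.

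**Step 1: the two leads.** Possible: "are felt unlikely to be related to the administration of the study TEST product, but the possibility cannot be ruled out with certainty". Unlikely: "are felt unlikely to be related to the administration of the study TEST product". The shared part is identical, and the difference is the rider in Possible. The item lists do differ: timing fits under Possible and does not under Unlikely, and a known pattern is present under Possible and absent under Unlikely. An event with fitting timing and no known pattern matches half of each contrast.

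**Step 2: code the items.** T = plausible timing, A = reasonable other explanation, K = known response pattern, R = recurs on rechallenge. Reading each list as jointly required:

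- Related = T, not A, K, R
- Probable = T, not A, K
- Possible = T, A, K
- Unlikely = not T, A, not K

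**Step 3: enumerate the 2 × 2 × 2 = 8 combinations of T, A and K.** The last column assumes no rechallenge.

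| T | A | K | All items required | Any one item enough |
|---|---|---|---|---|
| yes | no | yes | Probable (also Related if R) | Related, Probable, Possible |
| yes | yes | yes | Possible | all four |
| yes | no | no | none | all four |
| yes | yes | no | none | all four |
| no | yes | no | Unlikely | Possible, Unlikely |
| no | yes | yes | none | all four |
| no | no | yes | none | all four |
| no | no | no | none | Related, Probable, Unlikely |

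*All items required.* Only 3 of 8 combinations are assigned. Of the 4 with no known pattern, none reaches Possible or above and 1 reaches Unlikely. The two with plausible timing and no known pattern meet none of the four categories, and adding R changes nothing. An event with good timing, no other explanation and recurrence on rechallenge would still miss Possible.

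*Any one item enough.* Every combination meets between two and four categories. An event with plausible timing and no known pattern meets all four, so the scale does not discriminate.

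The all-items reading is the more natural one. It keeps the categories distinct, and the only item separating Related from Probable is rechallenge, which would have no purpose if any item sufficed.

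**Step 4: follow one event.** Take a wound infection shortly after the first application. The timing fits, the ulcer itself could explain it, 8.1 reports that infection has not been seen, and infection is not among the potential concerns named there. So T = yes, A = yes, K = no. With all items required it misses Related and Probable (A and K), Possible (K) and Unlikely (T). Not related does not fit cleanly: the event meets the timing item of the higher categories, and nothing shows sufficiently that its cause lies elsewhere. Not assessable does not describe it either, since the information need be neither insufficient nor contradictory. Its category is undefined.

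**Step 5: outputs affected.** Affected are the related-event subset in 10.3 and, in 9.4, the follow-up of serious events and the reporting of serious events after the study. Not affected are the tabulation of all treatment-emergent events, their summary by severity, the listings of serious events and of discontinuations due to adverse events, and the 24-hour report of serious events during the study.

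**The case against.** The best case for the protocol has four parts.

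- **Judgement comes first.** Each category rests on medical consideration, and the items are introduced permissively, without the word 'all'. An investigator may choose a higher category. This stands: it rules out saying that the scale *cannot* record a new reaction. It does not remove the ambiguity, because the permissive reading lets one event meet several categories.
- **Not observed is not the same as not known.** Section 8.1 names hypersensitivity, maceration and odor sensitivity, and the entry criteria exclude fish allergy (and, for venous ulcers, lidocaine allergy). A site could treat these as known patterns. This stands too, and it covers some of the likeliest local reactions. The gap is sharpest for reactions outside that list.
- **Possible and Unlikely can be told apart** by the rider and by opposite timing and pattern items. This is partly right. It works for events that satisfy one full list, but not for an event with fitting timing and no known pattern.
- **Harm is visible elsewhere.** All treatment-emergent events are tabulated whatever their attribution, and a randomized comparison of all events needs no causality judgement. This stands and limits the consequence to attribution.

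A reader might infer that a new reaction drops by default to Not related. The text does not support that. The default wording ("The AE does not meet any of the above criteria for relatedness") is not met by an event whose timing fits, and the second item of that category is not met either.

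**Conclusion.** The scale is badly specified for a product with no observed reactions. The overlap between the leads of Possible and Unlikely holds on any reading. The second defect takes one of two forms. If all items are required, a first-time reaction with plausible timing that is not among the concerns named in 8.1 has no defined category and may end up below the 10.3 cut. If any item is enough, it meets several categories at once. In both cases the related-event subset depends on the site's reading.

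The size cannot be given as a number of events, because the protocol states no expected reaction rate. What can be stated is the coverage: 3 of 8 combinations assigned under the all-items reading, with none of the 4 lacking a known pattern at Possible or above; and two to four categories per combination under the any-item reading.

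It would be tempting to conclude that the related-event table will be near zero whatever the true rate, or that it is biased in a known direction. That requires both that all items are jointly needed and that the concerns anticipated in 8.1 do not count as known. The protocol states neither. The supported conclusion is undefined attribution, with a risk of under-attribution. The conclusion does not extend to the causality-free safety summaries or to efficacy.

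**What to change.** In Protocol 9.3 and the eCRF completion guide:

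1. **Possible.** Replace the lead judgement of unlikely relation with wording such as 'may be related, although another cause may also be plausible'. Delete the known-pattern item. Make plausible timing enough, whether or not another explanation exists, unless Probable or Related is met.
2. **Probable and Related.** Change the pattern item to 'known or biologically plausible pattern'.
3. **All categories.** State for each whether all listed items are required.
4. **Unlikely and Not related.** Align them with the new Possible so that every event with plausible timing has a category. With these changes all 4 combinations with plausible timing are placed: Probable (or Related with rechallenge) when there is no other explanation and the pattern is known or plausible, and Possible otherwise.
5. **Section 10.3.** Keep the cut at Possible.

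The cost is a wording amendment and a short site instruction, best made before causality assessments accumulate. It changes no treatment, sample size or efficacy analysis. The downside is that somewhat more events will count as possibly related, so the related-event table will look less favourable.
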